6.1 Non-Study Eye

The non-study eye will be treated as per the standard of care at the investigator's discretion.

7 Patient Visits and Examination

7.1 Introduction

Patients will be assessed with respect to safety outcomes for which standardised procedures have been developed:

- BCVA by a trained technician will be undertaken
- Adverse event assessment
- Dilated fundal examination
- Central macular thickness by OCT

7.2 Patient Follow-up

Standard of care post-surgery visits will be conducted as per normal through the Outpatient Department, Sydney Eye Hospital. There will be no additional study-specific visits post-surgery. The Principal Investigator and/or Sub-Investigator will collect adverse events during these follow-up visits throughout the post-operative period (to twelve months).

8 Safety

8.1 Study Procedure Risks

The risks of this study are identical to the standard management for sub-macular bleeding except for one difference: the use of fluorescein sodium, a yellow dye, to track the movement of fluid under the retina and within the vitreous cavity. Fluorescein is used routinely to study the ocular surface and in performing ocular angiography (where it is injected intravenously, typically in concentrations of up to 10%). In conditions that cause bleeding underneath the retina, fluorescein will leak into the sub-retinal space in concentrations approaching 10% without any known detrimental effects.

We will be using a lower concentration to study the flow of fluid within the eye during the proposed procedure. This concentration has previously been shown to have no detrimental effect on nerve cells (Kato et al., 1983) or on human embryonic kidney cells (Salvetti et al., 2017). Higher concentrations have been reported for visually tracking tPA in routine care (Khan et al., 2017). There is a small risk of allergy to fluorescein and patients with a history of such allergy will be excluded from this study.

8.2 Adverse Event Reporting

Adverse Event definition: any untoward medical occurrence in a patient or clinical investigation subject administered a pharmaceutical product and that does not necessarily have a causal relationship with this treatment. An adverse event (AE) can therefore be any unfavourable and unintended sign (including an abnormal laboratory finding), symptom or disease temporarily associated with the use of a medicinal product, whether or not related to the medicinal product.

Examples of an AE include:

- Exacerbation of a chronic or intermittent pre-existing condition, including either an increase in frequency and/or intensity of the condition.
- New conditions detected or diagnosed after investigational product administration, even though it may have been present prior to the study.
- Signs, symptoms or the clinical sequelae of a suspected interaction.
- Signs, symptoms or the clinical sequelae of a suspected overdose of either investigation product, or of a concurrent medication (overdose per se should not be reported as an AE/SAE).

This trial is being carried out in the facilities of a primary ophthalmic centre, with extensive experience in vitrectomy surgery. The medical staff is well-experienced in dealing with all adverse events associated with vitrectomy surgery.

Adverse events will be collected from the date of surgery. The incidence of adverse events will otherwise be recorded throughout the duration of the study. These will be graded by the Principal Investigator as mild, moderate or severe.

Serious Adverse Event definition: any untoward medical occurrence that at any dose:

- Results in death
- Is life-threatening
- Requires inpatient hospitalisation or prolongation of existing hospitalisation
- Results in persistent or significant disability/incapacity
- Is a congenital anomaly/birth defect

For serious adverse events (SAEs) the relationship to the study drug will be graded as unrelated, possibly related, probably related or definitely related. SAEs will also be graded as expected or unexpected.

SAEs as defined by the International Conference on Harmonisation, Good Clinical Practice (ICH-GCP) as per above, will be reported as SAEs to the site's approving HREC according to local requirements.

The following events are to be considered AEs, but not serious AEs and therefore reporting as SAEs is not required:

- Hospitalisations for elective surgery
- Hospitalisations for admissions of less than 24 hours in duration
- Hospitalisations to the emergency department not requiring admission within the hospital
- Care delivered as "hospital in the home" or similar in-home service (unless other SAE criteria are met, such as persistent disability)

8.2.1 Infectious Endophthalmitis

Infectious endophthalmitis can be an acute complication of vitrectomy surgery. Study patients are informed in detail about the symptoms of a developing infection and are advised to contact the study staff if they have any doubt about their eyes after surgery.

If patients present with infectious endophthalmitis, they will be treated according to the standard treatment. In general, this includes vitreous aspiration for gram stain, microbiology and resistance testing, followed by an injection of Vancomycin 1mg/ 0.1mL and Ceftazidime 2.25mg/ 0.1mL. Depending on the general situation, patients will be admitted to hospital or follow very closely as outpatients.

8.2.2 Retinal Detachment and Vitreous Haemorrhage

Patients presenting with a rhegmatogenous retinal detachment or massive vitreous haemorrhage following the surgery will be referred to the vitreoretinal service at Sydney Eye Hospital.

8.2.3 Damage to the Crystalline Lens

Acute opacification of the crystalline lens due to lens damage during surgery will be observed and treated surgically as appropriate.

8.2.4 Elevation of Intraocular Pressure

Patients with IOP measured \geq 30mmHg may be commenced on first line glaucoma medication.

8.2.5 Cataract Formation

The decision to perform cataract surgery will be made along conventional lines in consultation with the patient, taking into account the level of visual acuity in both eyes, the degree of lens opacification and the extent of functional disability.

8.2.6 Contraindication to use of Fluorescite

• Hypersensitivity to the active substance or to any of the excipients

Fluorescein sodium has been routinely used to perform ocular angiograms and study retinal disease for more than 50 years and is known to enter into the sub-retinal space of patients with common retinal pathology to act as a marker. It is not known to be associated with ocular toxicity, and has been previously shown to be non-toxic in chick neurones (Kato et al., 1983) and human embryonic kidney cells (Salvetti et al., 2017). It has been used previously in humans to track sub-retinal tPA delivery visually (Khan et al., 2017).

8.2.7 Contraindication to use of Actilyse

Actilyse is used routinely for the management of occlusive retinal vascular events, such as acute myocardial infarction and cerebral vascular accidents. It has been used for more than a decade in the management of sub-macular haemorrhage. Doses of up to 50 micrograms have been demonstrated to be safe in animal models (McAllister, 2006).

The investigator does not believe that fluorescein sodium will react adversely with sodium chloride or Actilyse. Its pH at 7.8 (5% solution) is within the ideal range for tPA activity and a combination has previously been reported as being used for sub-retinal injection in 6 patients in a study at Will Eye Hospital, Philadelphia (Khan, 2017). Any adverse outcome will be logged, though these are anticipated to be related to the disease process and/or the surgical procedure, rather than due to the study protocol itself.

8.3 Recording of AEs and SAEs

When an AE/SAE occurs, it is the responsibility of the investigator to review all documentation (e.g. hospital progress notes, laboratory, and diagnostic reports) relative to the event. The investigator/ site staff will then record all relevant information regarding an AE/SAE in to an electronic case report form (eCRF). Any SAE documentation forwarded to the TGA/HREC will be de-identified, maintaining patient anonymity. For each AE, start and stop dates, action taken, outcome, intensity (see Section 8.2) and the relationship to the study treatment and causality must be documented.

The investigator will attempt to establish a diagnosis of the event, based on signs, symptoms, and/or other clinical information. In the absence of diagnosis, the individual signs/ symptoms should be documented.

9 Statistical Considerations and Safety Monitoring

Although the small sample size will make statistical comparisons difficult, if at any point there is a suggestion of one method being clearly superior to the other (P = 0.01), the trial will be terminated early.

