1.2 Hypothesis

We hypothesise that the two-step approach will result in less reflux at the time of initiation of iatrogenic retinal detachment and during subsequent surgical steps.

2. Study Objectives

The overall objective of this study is to assess the reflux and retention of a therapeutic substance (tPA) delivered via two different techniques into the sub-retinal space to determine the optimum approach for sub-retinal injections.

3. Study Design

This is a randomised, controlled study in which patients diagnosed with sub-macular haemorrhage and who have been scheduled for sub-retinal tPA and pneumatic displacement will be randomly assigned (1:1) to either the two-step or the one-step group.

The target recruitment is 20 subjects. The sample size is based on the assumption that there is 10% (0.01mL) reflux of sodium fluorescein from blebs in both groups, and that there is a 60% wastage of fluid in the one-step procedure. The calculated sample size for a power of 0.80 and significance level of 0.05 is therefore 20 subjects.

We will review the results after the first 10 subjects. The trial will be terminated early if the appropriate statistical significance has been achieved (or in the event of a serious adverse event due to the study protocol).

Patients scheduled to undergo surgery for the displacement of sub-macular haemorrhage and who satisfy the eligibility criteria will be approached to participate in the study.

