3.2 Endpoints

Primary Outcome

• The primary endpoint is the amount of refluxed fluorescein sodium between the two-step and one-step approach.

Secondary Outcomes

- Time taken to perform the sub-retinal injection.
- Change in visual acuity at 3 and 12 months

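### Sections 3 and 9 give two different early-stopping rules, and neither adjusts the 0.05 level behind the sample size

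*Protocol*

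**What the plan says.** Protocol Section 3 (Study Design) sets the size of the trial: "The target recruitment is 20 subjects", and "The calculated sample size for a power of 0.80 and significance level of 0.05 is therefore 20 subjects". It then plans an interim review: "We will review the results after the first 10 subjects". The consequence is that "The trial will be terminated early if the appropriate statistical significance has been achieved". No interim level is given; the only level in that section is the 0.05 attached to the sample size. The same sentence also allows a stop for a serious adverse event due to the protocol.

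Section 9 (Statistical Considerations and Safety Monitoring) contains a second rule. The trial ends early "if at any point there is a suggestion of one method being clearly superior to the other (P = 0.01". It gives no schedule of looks and does not say on which outcome a method would be superior.

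Section 3.2 names refluxed fluorescein as the primary endpoint. Injection time and visual acuity are secondary. Neither stopping passage states a level for the final test after an interim look.

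**The concern.** One rule has a fixed time and no threshold; the other has a threshold and no fixed times. They can lead to different decisions on the same data. With p = 0.03 at 10 subjects, Section 3 stops the trial if its level is 0.05, while Section 9 does not. With p = 0.008 after 13 subjects, Section 9 stops the trial, while Section 3 has no look at that time.

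Section 9 also leaves open which outcome counts. Section 1.1 expects that the one-step method may be quicker but may waste more drug, so the arms could rank differently on reflux and on injection time.

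What is at stake is the 5% level on which the 20 subjects were computed. Each unadjusted chance to declare a difference adds to the false-positive probability. The trial is meant to guide the choice of technique in later studies, so the error rate behind a claim of superiority should be known.

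**Working it through.** **Inputs from the protocol.** N = 20, power 0.80, level 0.05 (Section 3; two-sided assumed, as sidedness is not stated). Allocation 1:1 by simple random bits (Sections 3 and 5.2). One review at 10 of 20, so half the information. A threshold of 0.01 at any time (Section 9). The primary endpoint is a continuous amount (Section 3.2).

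**Assumptions.** The interim level in Section 3 is either 0.01 or 0.05. The final test is at 0.05. The protocol names no test, so a pooled t-test on normal data is the base case, with two alternatives shown.

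**The plan's own figure.** Section 3 assumes "there is 10% (0.01mL) reflux of sodium fluorescein from blebs in both groups, and that there is a 60% wastage of fluid" in the one-step arm. Reading this as 10% versus 70% of patients, with mean proportion 0.4:

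n per arm = [1.96·√(2·0.4·0.6) + 0.8416·√(0.1·0.9 + 0.7·0.3)]² / 0.6² = 9.2, so 10 per arm and 20 in total.

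The figure of 20 is therefore reproduced with a single two-sided test at 0.05 and no allowance for an interim look. This reading treats volume fractions as proportions of patients, but the stopping question does not depend on that.

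**Two looks, normal theory.** The statistics at 10 and 20 subjects have correlation √(10/20) = 0.707. Overall error = 1 − P(|Z₁| < c₁ and |Z₂| < c₂).

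- c₁ = c₂ = 1.960 (0.05 at both looks): 8.3%.
- c₁ = 2.576 (0.01), c₂ = 1.960: 5.5%.

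**Simulation under no difference.** N = 20, simple random bits, final test at 0.05. The t-test columns use 300,000 trials and the exact rank test 20,000. Looks need at least two patients per arm. Overall two-sided error:

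| Rule | t-test, normal | t-test, lognormal | Exact rank test |
|---|---|---|---|
| Final test only | 5.0% | 3.5% | 4.5% |
| One look at 10, 0.01 | 5.6% | 4.0% | 4.9% |
| One look at 10, 0.05 | 8.5% | 6.2% | 6.8% |
| Every patient at 0.01, from 10 | 6.4% | 4.6% | 5.5% |
| Every patient at 0.01, from 4 | 8.1% | 6.5% | 5.5% |
| Both rules, looks from 4 | 10.1% | 7.9% | 7.0% |

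The rank test gives the same result from 4 as from 10 because no earlier look can reach 0.01. Its smallest two-sided p is 2/C(9,4) = 2/126 = 0.016 at 4 versus 5, and 2/C(10,5) = 2/252 = 0.0079 at 5 versus 5.

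**Levels that keep 5% with one look at 10** (normal theory): interim 0.01 with final 0.0452; O'Brien-Fleming 0.0052 with 0.0480. An interim at p < 0.001 with a final 0.05 gave 5.0% to 5.1% in simulation with the t-test.

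**The case against.** The strongest reply is that Section 9 supplies the number that Section 3 leaves open. On that reading there is one look at 10 at 0.01, and the excess is about half a percentage point with a t-test. With an exact rank test the total is 4.9%, because that test is conservative. This stands as far as it goes: the protocol nowhere sets 0.05 for the interim, so a reader who infers a flat 8% to 10% is taking the upper part of a range. But the reading works only by ignoring the words in Section 9 that allow a look at any time.

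A second reply is that boundaries commonly belong in the statistical analysis plan. That is true of the boundary values. Here the protocol itself fixes two rules that differ, and an analysis plan would have to override one of them.

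Third, Section 3 can fairly be read as meaning reflux, since the review follows a sample size built on reflux. The missing outcome is a fault of Section 9 only.

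A reader might also infer that an efficacy stop would cut off the secondary outcome "Change in visual acuity at 3 and 12 months". The documents do not say so. Follow-up runs on standard-care visits with adverse events collected to twelve months (Section 7.2), and final visual outcome can be checked against hospital records (Section 10.1).

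**Conclusion.** The point holds as a conflict between two stated stopping rules, with no adjustment of the 0.05 level for either. Its size depends on three things that the protocol leaves open: the interim level, the timing of looks, and the test. With a t-test and normal data every reading exceeds 5%, from about 5.6% (one look at 0.01), through about 6.5% to 8% (repeated looks at 0.01) and about 8.5% (one look at 0.05), to about 10% (both rules applied). With a rank test or strongly skewed data the range is about 4% to 8%, and the mildest readings stay below 5%. No single inflation figure should be quoted without its conditions. Loss of visual acuity follow-up is not part of the error.

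**What to change.** Replace the efficacy wording in Sections 3 and 9 with one rule: a single look after 10 patients, on the primary reflux endpoint, with a named test and a stated pair of interim and final two-sided levels that keeps 5% overall for that test. Delete the unlimited efficacy look in Section 9 and leave the safety stop unchanged.

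Workable pairs are 0.01 then about 0.045, or, if a t-test is used, O'Brien-Fleming 0.005 then 0.048, or p < 0.001 then 0.05. These come from normal theory or t-test simulation, so the pair should be confirmed by simulation for the chosen test at these small numbers.

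With an exact rank test the interim level must be at least 0.008 to be attainable at five per arm; 0.005 or 0.001 could never be met. Simple bit randomisation does not guarantee five per arm: at 4 versus 6 the smallest p is 2/C(10,4) = 2/210 = 0.0095, which still allows 0.01 but not 0.008.

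The cost is protocol wording and a smaller chance of stopping early for efficacy. A sentence saying that an efficacy stop ends recruitment only would be a useful clarification but is optional.

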9.1 Electronic Case Report Form (eCRF)

An eCRF will be completed for each patient for each study visit, summarising all of the screening and study data. Patients will be referred to by their study identification code, only to retain confidentiality.

10. Storage and Archiving of Study Documents

10.1 Storage and Identification

Data will be stored in re-identifiable form so that pertinent clinical data (baseline vision, diagnosis, final visual outcome) can be checked against hospital records. Data will be anonymised and pooled with

summary statistics presented. The unique participant code will be accessible and known only to the Principal Investigator, Sub-Investigator/s and study co-ordinator.

To ensure the security of information and avoid misuse, loss or unauthorised access to stored information during and after the study, printed information and paper case report forms will be stored in a locked office and computer files will be encrypted and stored on a password protected server.

10.1.1 Withdrawal

Should the participant wish to withdraw from the study, they will be free to do so and to decide what happens to their data. However, some analyses will be conducted on pooled samples, and if this is the case, that portion of the data will not be able to be destroyed.

10.2 Archiving

Information will be stored after the completion of the study for 5 years in order to allow for appropriate analysis and publication/dissemination of results.

10.3 Disposal

Data pertaining to the study would continue to be treated under the same protocols as described above in the event that the principal investigator ceases to be engaged at the planned organisation site. Information will be securely destroyed 5 years following cessation from any cause.

11. Administration Procedures

11.1 Ethical Considerations

This study will adhere to the tenets of the Declaration of Helsinki, the NHMRC National Statement on Ethical Conduct in Research Involving Humans (2007) and the Notes for Guidance on Good Clinical Practice as adopted by the Australia Therapeutic Good Administration (2000) and the ICH GCP Guidelines.

11.2 Human Research Ethics Committee

The protocol will be submitted for approval by the study site's Human Research Ethics Committee (HREC) and written approval obtained before volunteers are recruited and patients are enrolled. It is the responsibility of the investigator to report study progress to HREC as required or at intervals not greater than one year. The Principal Investigator or his nominee will be responsible for reporting any SAEs to HREC as soon as possible and in accordance with local guidelines.

11.3 Protocol Amendments

Protocol modifications that impact on patient safety or the validity of the study will be approved by HREC. If such amendments necessitate a change to the Informed Consent Form, the revised form prepared by the investigator must be approved by HREC.

The original signed copy of amendments will be kept in the study file with the original protocol. It should be noted that where an amendment to the protocol substantially alters the study design or the potential risks to the patients, each patient's consent to continue participation should be obtained.

